8.7. ASSESSMENT OF EFFECT OF VARIOUS DOSES OF SEL-110 ON PHARMACOKINETICS OF SEL-037

Effect of co-administration of various doses of SEL-110 on pharmacokinetics of SEL-037 PK parameters for serum concentrations or uricase activity for cohorts 1, 3, 5, 7, 11 (SEL-037 dose 0.2 mg/kg) and 2, 4, 6, 8, 10, 12 (SEL-037 dose 0.4 mg/kg) separately (SEL-110 dose in cohorts 1 and 2 will be set to 0) will be performed by a linear mixed-effect model:

$$PKparam(SEL - 037) = \alpha + s_i + \beta \times Dose(SEL - 110) + e_i$$

α : population mean intercept

β : population mean slope

s_i : random effect of subject i on the intercept, iid $N(0, \sigma_s^2)$

e_i : residual, iid $N(0, \sigma_e)$ for subject i

Statistical Analysis Plan

the PK parameters and dose of SEL-110 will not be log-transformed to allow inclusion of 0 dose of SEL-110 into the model

P value will be calculated for slope and intercept. If the p-value of the slope is less than 0.05, a direct relationship is declared. If p value for slope will be >0.05 the result will be interpreted as lack of effect of SEL-110 on pharmacokinetics of SEL-037.

SEL-110 co-administration effect will also be explored graphically with scatter plots of C_{max} , AUC_{0-last} and AUC_{0-inf} for SEL-037 serum concentrations or uricase activity vs dose levels of co-administered SEL-110 including 0 dose for placebo.

The example SAS code will be:

```
PROC MIXED DATA=data_set_name;  
CLASS treatment;  
MODEL PK Parameter = dose /DDFM=KR;  
LSMEANS dose / CL;  
RUN;
```

Additionally the effect of SEL-110 on PK of SEL-037 will be performed by comparison of data from Parts B vs Part C for treatment periods 4-5 using ANOVA model as described in the Section 8.6 of the SAP.

The contrasts will include:

- Cohort 13 treatment period 4 vs Cohort 11 treatment period 4
- Cohort 13 treatment period 5 vs Cohort 11 treatment period 5
- Cohort 15 treatment period 4 vs Cohort 11 treatment period 4
- Cohort 15 treatment period 5 vs Cohort 11 treatment period 5
- Cohort 15 treatment period 4 vs Cohort 13 treatment period 4
- Cohort 15 treatment period 5 vs Cohort 13 treatment period 5

Graphic presentation in the form of box plots will be also added to the exploratory analysis.

Statistical Analysis Plan

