Mean time response profiles for uric acid concentration raw values and %CFB at each time point for each Treatment period and cohort plotted against time for each Cohort separately with curves for all Treatment periods overlaid on one plot. BLQ values for uric acid concentration will be assigned 0 values for linear scales and 1/10 of LLOQ values for all time points for the graphic representation on log-linear scales only. Actual measured concentrations will be presented on both linear and log-linear scales while %CFB profiles will be presented on linear scale only.

Box plots for each derived PD parameter based on actual measurements and %CFB: CFB_{min}, AUE_{CFBlast}, TA_AUE_{CFBlast} will also be plotted by treatment.

Individual profiles for uric acid concentration absolute values and %CFB will be plotted for each Treatment period and cohort on a separate plot.

9.7. ASSESSMENT OF THE EFFECTS OF SEL-110 (RAPAMYCIN) AND SEL-037 (PEGSITICASE) ON PD PARAMETERS OF URIC ACID

Assessments done outside the assessment windows may be excluded from summarization. This will be determined prior to database lock.

The key PD parameters based on measured values and %CFB %CFB_{min}, AUE_{%CFBlast}, and TA_AUE_{%CFBlast} as well as uric acid concentration and %CFB on day 21 of each treatment period will be analyzed using linear mixed model for the response to SEL-110 dose levels co-administered with either 0.2 or 0.4 mg/kg of SEL-037 (the dose level of SEL-110 for Cohorts 1 and 2 will be assigned as 0). Additionally contribution of SEL-110 to the PD effect of SEL-037 will be tested to compare the following (test - reference). For PD

Statistical Analysis Plan

parameters based on actual measured values baseline concentration of uric acid will be incorporated in the model as covariate.

For Parts A and B following contrasts will be tested:

Cohort 3 Part A vs Cohort 1 Part A
Cohort 5 Part A vs Cohort 1 Part A
Cohort 7 Part A vs Cohort 1 Part A
Cohort 4 Part A vs Cohort 2 Part A
Cohort 6 Part A vs Cohort 2 Part A
Cohort 8 Part A vs Cohort 2 Part A
Cohort 10 Part A vs Cohort 2 Part A
Cohort 12 Part A vs Cohort 2 Part A
Cohort 1 Part A vs Cohort 2 Part A
Cohort 3 Part A vs Part B
Cohort 5 Part A vs Part B
Cohort 7 Part A vs Part B
Cohort 4 Part A vs Part B
Cohort 6 Part A vs Part B
Cohort 8 Part A vs Part B
Cohort 10 Part A vs Part B
Cohort 12 Part A vs Part B

For Part C (cohorts 13, 15, 17) additional contrasts will be:

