Cohort 13 treatment period 4 vs Cohort 11 treatment period 4
Cohort 13 treatment period 5 vs Cohort 11 treatment period 5
Cohort 15 treatment period 4 vs Cohort 11 treatment period 4
Cohort 15 treatment period 5 vs Cohort 11 treatment period 5
Cohort 15 treatment period 4 vs Cohort 13 treatment period 4
Cohort 15 treatment period 5 vs Cohort 13 treatment period 5

Cohort 17 treatment period 4 vs Cohort 11 treatment period 4
Cohort 17 treatment period 5 vs Cohort 11 treatment period 5
Cohort 17 treatment period 4 vs Cohort 13 treatment period 4
Cohort 17 treatment period 5 vs Cohort 13 treatment period 5

Cohort 17 treatment period 4 vs Cohort 15 treatment period 4
Cohort 17 treatment period 5 vs Cohort 15 treatment period 5

Statistical Analysis Plan

Unstructured variance-covariance matrix will be used. If the model cannot converge or unable to make hessian positive definite, compound symmetry or other variance-covariance matrices will be explored and used.

Example SAS code will be:

```
PROC MIXED DATA=data_set_name;  
CLASS subject_id treatment;  
MODEL loge(PD Parameter) = treatment /DDFM=KR;  
RANDOM subject_id / TYPE=UN;  
LSMEANS treatment / DIFFS CL;  
RUN;
```

1. The following hypotheses will be tested:

- $H_{01}: \mu_T/\mu_R \leq 80\%$ vs. $H_{A1}: \mu_T/\mu_R > 80\%$
and
- $H_{02}: \mu_T/\mu_R \geq 125\%$ vs. $H_{A2}: \mu_T/\mu_R < 125\%$

If the 90% confidence interval (CI) for the geometric mean ratio (GMR) is within (80% - 125%) for any of the contrasts for C_{max} , AUC_{0-t} and AUC_{0-inf} , the null hypotheses, that is H_{01} and H_{02} , will be rejected and we will conclude that the Test (T) is equivalent to the Reference (R).

2. If bioequivalence cannot be established in step 1 above, the following hypothesis will be tested to explore noninferiority (1-sided test):

- $H_{01}: \mu_T/\mu_R \leq 80\%$ vs. $H_{A1}: \mu_T/\mu_R > 80\%$

If the lower 90% CI bound for the GMR is greater than 80% for C_{max} , AUC_{0-t} and AUC_{0-inf} , H_{01} will be rejected and we will conclude that the new therapy (T=Test) is no worse than the old therapy (R=Reference).

The formula for calculation of the estimated ratio between the test and reference and the $(1-2*\alpha)*100\%$ CI of the ratio is given below.

Difference = Estimate of difference between test and reference least square means

Statistical Analysis Plan

$$Ratio = 100 \times e^{Difference}$$

(1-2* α)*100% CIs for the Ratio:

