$$Lower = 100 \times e^{(LowerBound (1-2*\alpha)\%CIs for theDifference)}$$

$$Upper = 100 \times e^{(UpperBound (1-2*\alpha)\%CIs for theDifference)}$$

GMR ratio outside equivalence criteria 80-125% will demonstrate (1) dose effect SEL-110; (2) synergy or additive effect of SEL-110 administration on PD by SEL-037. P-values will be generated for all contrasts. Values of $p < 0.05$ will indicate statistical significance of the effect.

The results of the comparisons will be graphically illustrated using box plots for Part A/B and comparison between Part C and B separately.

Correlations between PD endpoints (C_{min} , CFB_{min} , $AUE_{CFBlast}$, and $TA_AUE_{CFBlast}$) and PK parameters (C_{max} , AUC_{0-last} and AUC_{0-inf}) for both SEL-110 and SEL-037 will be explored using Spearman correlation analysis. The correlations for Part C treatment periods will be presented in the separate table.

The correlation between each of these PK (C_{max} , AUC_{0-last} and AUC_{0-inf}) and PD (C_{min} , CFB_{min} , $AUE_{CFBlast}$, and $TA_AUE_{CFBlast}$) parameters will also be explored and presented in a scatter plot with a regression line on it using simple linear regression which will have PK parameter as dependent variable and PD parameter as independent variable. The additional plots will be created for the Part C.

Example SAS code will be:

```
PROC GLM DATA=PKPDDATA;  
MODEL PD_parameter = PK_parameter;  
RUN;
```

Statistical Analysis Plan

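### SAP 8.7 and 9.7 turn non-significance into no effect, tie equivalence rules to the wrong parameters, log values that can be negative or zero, and leave the SEL-110 effect rule unjoined to p<0.05

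*SAP*

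**What the plan says.** **SAP 8.7** regresses SEL-037 PK parameters on SEL-110 dose, untransformed, separately for the 0.2 and 0.4 mg/kg SEL-037 cohorts, with Cohorts 1 and 2 at dose 0. Its rule for a non-significant slope is: "If p value for slope will be >0.05 the result will be interpreted as lack of effect of SEL-110 on pharmacokinetics of SEL-037". The example code fits "MODEL PK Parameter = dose /DDFM=KR" and then requests "LSMEANS dose / CL". Dose is not in the CLASS statement, and no interval for the slope is requested.

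**SAP 9.7** analyses %CFBmin, AUE%CFBlast, TA_AUE%CFBlast, and Day-21 uric acid and Day-21 %CFB. The example code models the natural log of the PD parameter, and the reported ratio is 100 times the exponential of the difference. The equivalence rule begins "If the 90% confidence interval (CI) for the geometric mean ratio (GMR) is within (80% - 125%) for any of the contrasts for" and then names Cmax, AUC0-t and AUC0-inf. The non-inferiority rule names the same three. The section then states that "GMR ratio outside equivalence criteria 80-125% will demonstrate (1) dose effect SEL-110; (2) synergy or additive effect of SEL-110 administration on PD by SEL-037". Directly afterwards it says that p-values will be produced for every contrast and that p<0.05 "will indicate statistical significance of the effect". One listed contrast is "Cohort 1 Part A vs Cohort 2 Part A", in which neither cohort receives SEL-110.

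**Related definitions.** SAP 9.1 defines %CFB as change divided by baseline, times 100. SAP 9.3 defines AUE%CFBlast as an absolute value but does not say so for TA_AUE%CFBlast. SAP 9.3.1 sets uric acid below the quantification limit to zero. SAP 8.5 sets a 90% level in its code; the 9.7 code sets none.

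**The concern.** These rules produce the statements on the PK and PD of SEL-037 with and without SEL-110, which is a secondary objective.

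- **8.7:** a p-value above 0.05 in small cohorts is mostly a statement about precision. The SAP attaches a substantive conclusion to it, yet 8.7 gives no margin and SAP 3.6 gives no power basis.
- **9.7, endpoints:** as worded, no equivalence or non-inferiority rule applies to anything the section analyses.
- **9.7, scale:** two of the named endpoints are negative whenever the drug works, so they have no log and no geometric mean ratio.
- **9.7, effect claim:** two criteria stand side by side, a GMR outside 80-125% and p<0.05, with no precedence. A ratio below 80% and one above 125% count alike, and additive effect is not separated from synergy.

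The report could therefore state that SEL-110 does not affect SEL-037 PK because cohorts were small, or that SEL-110 has a PD effect on the strength of noise.

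**Working it through.** **No plan figure to reproduce.** Neither document gives a power, error rate or design effect for 8.7 or 9.7, or any CV for SEL-037 PK or uric acid. The only variability derivable is for SEL-110 in whole blood (protocol Table 7, SD/mean): 12-48% for AUC0-last (for example 4912.06/10332.1 = 47.5%) and 18-33% for Cmax. That is a different analyte, so CVs of 20, 30 and 50% below are assumptions.

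**Cohort size.** Protocol 6.2 and SAP 3.7 plan about 100 subjects in 11 Part A/B cohorts of 6-20: 100/11 ≈ 9 each. Twenty in every cohort would need 11 × 20 = 220. I use 6 and 10.

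**(1) 8.7 slope.** Doses are 0, 0.05, 0.08, 0.10, 0.15 mg/kg (0.2 set), plus 0.125 in the 0.4 set. Assume a true 25% change from 0 to 0.15 mg/kg, SD = CV × mean at dose 0, one observation per subject and a two-sided 0.05 test. The noncentrality is (0.25/0.15) × √Sxx / CV. For the 0.2 set with 6 per cohort, Sxx = 0.0751 and df = 28. At CV 30% the noncentrality is 1.667 × 0.2741/0.30 = 1.52 and power is 31%, so lack of effect is reported in 69%.

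| Reported as lack of effect | CV 20% | CV 30% | CV 50% |
|---|---|---|---|
| 6 per cohort | 33-40% | 64-69% | 84-86% |
| 10 per cohort | 12-18% | 45-51% | 76-79% |

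Ranges span the 0.4 and 0.2 sets. If three periods are averaged with an assumed within-subject correlation of 0.5, the variance is multiplied by (1 + 2 × 0.5)/3 = 0.667. The CV 30% figures become 50-56% and 28-34%.

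**(2) Endpoint names.** None of Cmax, AUC0-t and AUC0-inf appears among the five 9.7 endpoints.

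**(3) Log scale.** Protocol 4.3.2.3 reports that uric acid in every Phase 1 SEL-212 subject fell below 0.1 mg/dL within 24 hours. With an assumed baseline of 8 mg/dL, %CFB = (0.1 − 8)/8 × 100 = −98.75, which has no log. A Day-21 uric acid carried in as zero has none either. Very low Day-21 values are plausible, because protocol 6.3.1 requires 1.0 mg/dL or less for further dosing in the SEL-110 cohorts.

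**(4) 9.7 effect sentence, point-estimate reading.** With SD(log) = √ln(1+CV²), SE = SD√(2/n) and no true difference, P(outside) = 2[1 − Φ(ln 1.25/SE)]. At CV 30% and 6 v 6, SD = 0.2936 and SE = 0.1695. Then 0.2231/0.1695 = 1.317 and P = 19%.

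| GMR outside 80-125%, no true difference | CV 20% | CV 30% | CV 50% |
|---|---|---|---|
| 6 v 6 | 5% | 19% | 41% |
| 10 v 10 | 1% | 9% | 29% |

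In simulation, the GMR is outside the bounds with p≥0.05 in 14% (CV 30%) and 37% (CV 50%) at 6 v 6, and in 4% and 24% at 10 v 10. At CV 15% the conflict reverses: p<0.05 with the GMR inside the bounds in 4-5%. Requiring p<0.05 as well leaves about 5% or less. These figures are for between-cohort contrasts, not the eight Part A v Part B contrasts within a cohort.

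**Contrasts in 9.7:** 9 between cohorts + 8 within + 12 for Part C = 29.

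**The case against.** The strongest defence is that this is exploratory work. The protocol's PK/PD plan is largely descriptive, SAP 9.7 speaks of exploring non-inferiority, and the missing confidence level, the `LSMEANS` line and the log all sit in example code. Part of this stands: the text does specify a 90% CI, so the missing level alone is minor. But the ratio formula in the body of 9.7 depends on the log scale, and the conclusions are worded as firm statements about a secondary objective.

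Four stronger readings are tempting, and the documents do not support them.

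- *9.7 has no p-value condition.* It has one, in the sentences after the effect statement. The defect is that the two are not joined. The 5-41% figures need a reader to act on the GMR alone.
- *The log model fails for every 9.7 endpoint.* AUE%CFBlast is an absolute value and is not affected. TA_AUE%CFBlast is unclear. The zero problem for Day-21 uric acid is conditional, because SAP 9.3.1 does not name this model.
- *The non-inferiority rule points the wrong way for uric acid.* The SAP does not apply that rule to uric acid. The direction would be wrong only if it were carried over unchanged.
- *Errors are large whatever the variability.* At CV 12%, lack of effect would be reported in only 2-4% at 6 per cohort; at CV 15%, the point-estimate reading errs in about 1%. The documents give no basis for CVs of 80-100%.

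Averaging over periods would help somewhat, but subjects stopped under the Day-21 rule have no later periods.

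**Conclusion.** The point holds, and should be fixed before database lock. Four defects follow from the text alone: the lack-of-effect inference in 8.7; the wrong parameter names in the 9.7 rules; a log model that cannot take %CFBmin, Day-21 %CFB or zeros; and an effect statement without interval, direction or link to p<0.05.

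The size of the first and last depends on assumed CVs, an illustrative 25% change, one observation per subject and 6-10 per cohort. On those terms, 8.7 would miss a real change in roughly one in eight to six in seven analyses. The point-estimate reading of 9.7 would put a null contrast outside the bounds in 1-41%. A reader might infer that the trial's main conclusions are at risk; they are not, since the primary objective is safety and tolerability.

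**What to change.** **SAP 8.7.** Delete the lack-of-effect sentence and call p>0.05 inconclusive. Replace the `LSMEANS` request with the slope estimate and its CI. Conclude no relevant effect only if the 90% CI for the change at 0.15 v 0 mg/kg lies within a margin set before database lock. Because the model is untransformed, a percentage change is a ratio to the dose-0 mean, and a Fieller interval serves.

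**SAP 9.7.**
- Replace Cmax and AUC with the PD endpoints analysed.
- Keep the log/GMR analysis for strictly positive endpoints such as AUE%CFBlast, and state whether TA_AUE%CFBlast is absolute. Analyse %CFBmin, Day-21 %CFB and any endpoint containing zeros as untransformed differences with CIs, with no equivalence claim unless a margin is set beforehand.
- Use one joined rule. Claim an effect only if two-sided p<0.05 (95% CI excludes no difference), and state its direction. Claim equivalence only if the whole 90% CI (`ALPHA=.1`) is within 80-125%. If neither holds, report inconclusive.
- If non-inferiority is applied to raw uric acid, use the upper bound, because lower is better.
- Make SEL-110 statements only for contrasts that differ in SEL-110, which excludes Cohort 1 v Cohort 2. Use the section's own term, contribution, instead of synergy. Label p-values nominal across the 29 contrasts.

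**Cost.** A few lines of text and code, and more inconclusive results. With no true effect, CV 30% and an 80-125% margin, the 8.7 conclusion of no relevant effect would be reached in about 1% at 6 per cohort and 9-17% at 10; at CV 50%, in about 2% or less. In 9.7, equivalence at 6 v 6 would be shown in 20/2/0% at CV 20/30/50%. That reflects what cohorts of this size can support.

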10. ANALYSIS OF IMMUNOGENICITY

Immunogenicity endpoints include screening and confirmation results for IgG antibodies to pegsiticase, uricase, and IgM anti-PEG antibody. The titer for the anti-pegsiticase IgG antibodies will be determined during confirmation assay. The titer for the anti-uricase IgGs will be reported for positive samples. Preliminary concentration for anti-PEG IgM will be estimated in screening assay and confirmed in confirmation assay using multiple dilutions.

The Parts A/B (Treatment periods 1-3 and 4-5 for cohorts 1-8, 10-12 respectively) will be presented together separately from Part C (cohorts 13, 15) unless necessary for comparative analysis.

10.1. COLLECTION SCHEDULE

Cohorts 1-8, 10, 11, 12

Period	Day	Time from start of dose for saline, h	Time from start of dose for SEL-037, h
1-3	0	0	-1 (0)
	7	168	167
	14	336	335
	21	504	503
	28*	672	671
4-5	0		0
	7		168
	14		336
	21		504
	28**		672
	30***		720

* - pre-dose for next Treatment period

** - immunogenicity point for Treatment period 4 as pre-dose for Treatment period 5

*** - last point for Treatment period 5 only

Cohorts 13, 15

Period	Day	Time from start of dose for saline, h	Time from start of dose for SEL-037, h
1-5	0	0	-1 (0)
	7	168	167
	14	336	335
	21	504	503
	28*	672	671
	30**		720

Statistical Analysis Plan

- * - pre-dose for next Treatment period
- ** - last point for Treatment period 5 only

10.2. DERIVED AND IMPUTED DATA

No imputation of missing immunogenicity data will be performed.

10.3. DATA SUMMARIZATION

Tables summarizing the frequency of the occurrence of ADAs by dose and by time point with overall summary per treatment will be produced for all cohorts separately and combined. The time of onset of immunogenicity, duration and number of resolved ADA cases will be summarized.

10.4. DATA PRESENTATION FOR IMMUNOGENICITY

Immunogenicity sampling times and results will be listed for safety analysis set outlined in Section 5.2 in this SAP. Immunogenicity endpoints include occurrence of anti-PEG, anti-pegsiticase, and anti-uricase specific antibodies based on screening assay and the titer for the anti-drug antibodies as identified in the confirmation assay.

Frequency of occurrence of antibodies by study day and overall by cohort, time of onset immunogenicity and time of resolution of immunogenicity will be calculated and summarized by treatment in summary tables. Time of onset is defined as 1st time point with positive ADA result; time of resolution is defined as 1st time point when previously observed positive ADA result returns to baseline. Titer of antibodies against PEG, uricase and pegsiticase will be listed. The effect of possible antibody responses on PK and PD parameters will be evaluated descriptively.

Cumulative positive ADA result for subject will be defined for each treatment period separately as at least one positive antibody post-dose time point for each Treatment period and Overall. The ADA positive subjects will be also stratified by the titer values for anti-pegsiticase and anti-uricase. The limits for titer values for low, moderate and high range will be identified based on percentiles after review of actual data (for example ≤ 30 percentile - low, 31-70 percentile - moderate, 71-100 percentile - high). Cumulative negative result will be defined as negative ADA result at all time points for a subject during each Treatment period.

Following tables will be produced to evaluate effect of immunogenicity on PK:

Statistical Analysis Plan

- Descriptive statistics of the key PD parameters based on measured values and $\%CFB$, $\%CFB_{\min}$, $AUE_{\%CFBlast}$, and $TA_AUE_{\%CFBlast}$ as well as uric acid concentration and $\%CFB$ on day 21 of each treatment period for ADA positive and negative, ADA low, moderate and high titer groups including Q1, Q3, 5, 10, 90 and 95 percentiles. The data will be presented by cohort and overall.
- Descriptive statistics of the key PK parameters based on measured values and C_{\max} , T_{\max} , AUC_{0-last} , and AUC_{0-inf} for ADA positive and negative, ADA low, moderate and high titer groups including Q1, Q3, 5, 10, 90 and 95 percentiles. The data will be presented by cohort and overall.
- Frequency summary of subjects for ADA positive and negative results on day 21 as well as titer groups stratified by stopping rule from the protocol - subjects who had serum uric acid (sUA) value less than or equal to 1.0 mg/dL at any of the Day 21 visits and were eligible for the next dosing of SEL-212 (or SEL-037) vs subjects who had > 1mg/dL sUA at this time point. The results for the treatment periods will be time-matched between immunogenicity testing and sUA concentration measurement. The data will be presented by cohort and overall.
- Additionally model for the evaluation of the dose effect of SEL-110 and SEL-037 on PD results described in the section 9.6 of the SAP may be repeated with additional covariate for immunogenicity (cumulative positive, negative, positive low, high and moderate titer) to evaluate if immunogenicity had an additive or individual effect on the sUA as compared to the dose effect.

Following plots will be presented for immunogenicity and PK parameters:

Box and whiskers plot for comparison of CL values for SEL-037 (pegsiticase), C_{\max} , T_{\max} , AUC_{0-last} , and AUC_{0-inf} derived using both PK concentrations and uricase activity between subjects with cumulative positive and negative immunogenicity results for each antigen separately (PEG, uricase or pegsiticase) by Cohort with varying doses of SEL-110 and overall. The additional plots will be created for the Part C.

Following plots will be presented for immunogenicity and PD parameters:

Box and whiskers plot for comparison of C_{\min} , CFB_{\min} , $AUE_{CFBlast}$ and $TA_AUE_{CFBlast}$, $\%CFB_{\min}$, $AUE_{\%CFBlast}$ and $TA_AUE_{\%CFBlast}$ values for uric acid between subjects with cumulative positive and negative immunogenicity results for each antigen separately (PEG, uricase or pegsiticase) by cohort and overall.

Statistical Analysis Plan

10.5. ASSESSMENT OF THE EFFECTS OF IMMUNOGENICITY OF PHARMACOKINETICS OF SEL-037(PEGSITICASE) AND ON PD PARAMETERS OF URIC ACID

The effect of possible antibody responses on PK parameters will be evaluated descriptively.

Immunogenicity results will be compared descriptively between treatments using frequency of each type of ADA as main parameter as well as the time of onset of immunogenicity.

The CL for SEL-037 (pegsiticase), C_{max} , T_{max} , AUC_{0-last} , and AUC_{0-inf} derived using both PK concentrations and uricase activity will be compared between subjects with cumulative negative and cumulative positive ADA results by Treatment period and cohort and overall for each cohort individually in the descriptive statistics table.

Similarly, PD parameters C_{min} , CFB_{min} , $AUE_{CFBlast}$, $TA_AUE_{CFBlast}$, $\%CFB_{min}$, $AUE_{\%CFBlast}$ and $TA_AUE_{\%CFBlast}$ will be compared between subjects with cumulative negative and cumulative positive ADA results by Treatment period and cohort and overall for each cohort individually in the descriptive statistics table.

No statistical inferences will be done for the comparisons.

Statistical Analysis Plan

